This study is a prospective, randomized controlled trial that will study the postoperative clinical outcomes of levothyroxine supplementation in delayed recovery or prolonged ventilation patients post cardiac surgery.

Randomization will be performed using a computer-generated randomization sequence and allocation concealment to be maintained all through the time of procedure, by using opaque, numbered, and sealed envelopes.

The study protocol will receive ethical approval from the Research Ethical Committee/ Institutional Review Boards, Faculty of Medicine Ain Shams University.

Informed consent will be obtained from each patient before patients' allocation.

Type of the study: prospective randomized clinical trial study protocol.

Study Setting: The operating theaters and ICU of Cardiothoracic institute of Ain Shams University Hospitals.

Study period: one year.

Sample Size:

Using PASS 15 program for sample size calculation, setting power at 80% and alpha error at 0.05, it is estimated that sample size of 25 patients per group total 50 patients can detect an effect size .80 or the difference between two groups regarding different qualitative outcome measures using two-sized a z test

Study population:

Inclusion criteria:

- Age group: Adult patients from age of 45 to 70 years.

Hypothyroidism was reported to be strongly related to cardiovascular disease, respiratory complications, neurological complications, and a significant difference in ventilator weaning time [3].

- Sex: Both sexes
- Elective, urgent and emergency open heart surgeries.

Exclusion criteria:

- Patients refuse to give informed consent.
- Patient younger than 45 years old, older than 70 years old.

- Off pump patients.
- Patients known hypothyroidism on levothyroxine supplementation.
- Patients known hyperthyroidism on Carbimazole.

Sampling method:

Patients will be randomly allocated by computer generated randomization into two groups A and B:

- **Group A (Study group):** patients receiving oral supplementation of levothyroxine.
- **Group B (Control):** patients receiving Placebo drug.

Anesthetic management:

Full standard preoperative assessment for cardiac surgery will be done for all patients included in the study before planned procedures.

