Premedication will be given according to standard protocol in cardiac anesthesia. Routine monitoring included a five-lead electrocardiogram, pulse oximeter and invasive blood pressure. Anesthesia will be induced with midazolam 0.02mg/kg and fentanyl 2-5 microgram /kg and muscle relaxation were achieved cisatracurium 0.15 mg/kg intravenous. After tracheal intubation, central venous line and TEE inserted, then anesthesia will be maintained throughout the procedure with morphin20 microgram/kg /min, cisatracurium 2mg/kg/min and sevoflurane 2%. Ventilation will be adjusted to maintain end-tidal carbon dioxide in the range of 30-40 mmHg.

On ICU arrival all patients will be subjected to standardized management as per institutional protocols. Patients who show signs of delayed recovery defined as either prolonged ventilation for 48 hours or delayed conscious level recovery for 48 hours despite exclusion of muscle relaxants and/or sedative drugs. Those patients will undergo CT brain, CT chest and neurological examination to exclude structural damage as per institutional protocols. Also, metabolic profile screening including full kidney function, full liver function, electrolyte and thyroid profile (TSH, free T3, free T4) to exclude correctable metabolic abnormalities.

Patients then divided into two groups: group A will receive levothyroxine via Ryle, dose of 25 to 50 ug/ day according to BMI, while group B will receive placebo in form of inert starch tablet.

Daily assessment of conscious level according to Glasgow Coma Scale (GCS) and spontaneous breathing trial by ICU consultant till ICU discharge.

Assessment of thyroid profile (free T3, free T4, TSH) before hospital discharge.

Endpoints of the study:

Primary end point:

1. Improvement of Glasgow coma scale and spontaneous breathing trial before ICU discharge.

Secondary end points:

1. Total ventilation time.
2. Total ICU stay.
3. Total hospital stay.
4. Total amount of inotropic support.
5. Improvement of cardiac function by echocardiography.

Ethical considerations:

The study protocol will receive ethical approval from the Research Ethical Committee, Faculty of Medicine Ain Shams University.

Informed consent will be obtained from each patient before patients' allocation.

Sample Size Calculation

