Using PASS 15.0 (NCSS LLC), detecting an effect size of 0.80 in GCS change ($\alpha = 0.05$, power = 80%) required 25 patients per arm. To ensure adequate power for secondary endpoints and allow for dropouts, we enrolled 35 patients per group (total $n = 70$).

Statistical Analysis

Analyses adhered to the intention-to-treat principle. Continuous variables are reported as mean \pm SD or median (IQR) and compared using Student's t-test or Mann-Whitney U test, as appropriate. Categorical variables are expressed as counts (%) and compared by χ^2 or Fisher's exact test.

- **Primary analysis:** Linear mixed-effects regression modeled GCS trajectories over time, with group, time, and their interaction as fixed effects and patient as a random effect.
- **Time-to-event outcomes:** Kaplan-Meier curves and Cox proportional hazards models yielded hazard ratios (HRs) and 95% confidence intervals (CIs).
- **Mediation:** The Sobel test quantified the proportion of EF preservation attributable to changes in free T3.

- **Sensitivity and subgroup analyses:** Inverse probability weighting assessed robustness; prespecified subgroups included diabetes status and CPB duration > 200 minutes.

All tests were two-tailed with $\alpha < 0.05$. Statistical analyses were performed using R v4.3.1 with the lme4, lavaan, and survminer packages.

4. REFERENCES (Maximum 20 references)

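### The primary outcome is observed only until ICU discharge and has no common day, so the measured effect depends on when patients leave ICU

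*Combined protocol and SAP*

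**What the plan says.** All references are to the combined protocol and SAP.

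- Methodology (section 3), ICU management: "Daily assessment of conscious level according to Glasgow Coma Scale (GCS) and spontaneous breathing trial by ICU consultant till ICU discharge". Patients enter the randomised comparison because they are still ventilated, or have not regained consciousness, at 48 hours.
- Endpoints of the study, primary end point: "Improvement of Glasgow coma scale and spontaneous breathing trial before ICU discharge". Ventilation time and length of ICU stay are secondary end points.
- Sample Size Calculation: the basis is "detecting an effect size of 0.80 in GCS change", with no day attached to the change.
- Statistical Analysis, primary analysis: "Linear mixed-effects regression modeled GCS trajectories over time", with fixed effects for arm, time and arm-by-time and a patient-level random effect. No contrast day, horizon, or rule for discharge or death is stated.

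No GCS or spontaneous breathing trial (SBT) assessment is planned after ICU discharge. The only study measurement dated later is the repeat thyroid profile before the patient goes home.

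**The concern.** A patient admitted to the comparison because of failure to wake or wean will usually leave ICU after doing so. The documents give no discharge criteria, so this is inferred from the entry rule and from ICU stay being listed as an outcome. If it is right, recovery closes the observation window, and an effective drug closes it earlier in its own arm.

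The plan then admits two readings of its primary result. Under the endpoint wording, each patient is compared at his or her own discharge. Slow controls also tend to be awake by then, so much of a real difference in speed disappears. Under the mixed model, time is on a common axis, but the recovered state of early leavers is not observed. A straight-line arm-by-time slope also names no day to which the result applies. In both cases the number reported depends partly on how soon the unit discharges recovered patients.

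**Working it through.** **1. The plan's own figure.** Inputs: "setting power at 80% and alpha error at 0.05"; "All tests were two-tailed"; a z test ("using two-sized a z test"); standardised effect 0.80. Per arm, n = 2(1.960 + 0.842)² / 0.80² = 24.53, so 25. This agrees with "required 25 patients per arm". Power at 0.80 by z test is 80.7% with 25 per arm and 91.7% with the 35 per group enrolled. The arithmetic is sound. What is missing is the day on which the change is 0.80 SD.

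**2. A hand example.** None of these values is in the documents. Take baseline GCS 8, recovery of 0.5 points/day on control and 1.6 × 0.5 = 0.8 on drug, a cap of 15, and discharge after two consecutive days at 14 or more.
- Day 7: control 8 + 7 × 0.5 = 11.5; drug 8 + 7 × 0.8 = 13.6; difference 2.1.
- At discharge: control on day 13, 8 + 13 × 0.5 = 14.5; drug on day 9, 8 + 9 × 0.8 = 15.2, capped at 15; difference 0.5.

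**3. The same setting with variation between patients.** 35 per arm, baseline SD 2, log-normal recovery slopes with the medians above, 28-day limit, no deaths, 1,000 simulated trials.

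| Comparison | Difference (points) | SD units | t-test power |
|---|---|---|---|
| Change to day 7, everyone | 1.3 | 0.62 | 71% |
| Change to last ICU score | 0.3 | 0.14 | 10% |
| Change to last ICU score, 14-day limit | 0.8 | – | 37% |

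A z approximation, power = Φ(d√17.5 − 1.96) plus the opposite tail, gives 74% at d = 0.62 and 9% at d = 0.14, which is consistent. Mean GCS follow-up was about 9.7 days on drug and 13.8 on control.

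**4. The mixed model in that setting.** Following everyone to day 7 gives an arm-by-day slope of 0.18. Data cut at ICU discharge give 0.12 to 0.14 with a random intercept and 0.28 with a random slope. The direction of the error depends on a choice the plan leaves open. Power with the random-slope model was not reduced.

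**5. A second setting, changing only discharge timing.** Exponential recovery towards 15 at 0.35 v 0.20 per day, discharge a set number of days after GCS first reaches 14, 14-day maximum, random-intercept model, 400 trials per row.

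| Delay (days) | Slope, cut at discharge | Last ICU score difference | Day-7 difference | Left before day 7, drug v control |
|---|---|---|---|---|
| 0 | 0.229 | 0.24 | 0.94 | 75% v 44% |
| 1 | 0.209 | 0.41 | 0.95 | 64% v 34% |
| 3 | 0.143 | 0.45 | 0.94 | 33% v 12% |
| 6 | 0.061 | 0.46 | 0.96 | 0% v 0% |

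The drug effect is the same in every row. The slope changes almost fourfold (0.229 / 0.061 = 3.75), while the day-7 contrast hardly moves. Following everyone to day 14 gives a slope of about −0.03, because the faster arm reaches the ceiling first. Longer collection alone therefore does not repair a linear slope.

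**6. No drug effect.** With equal recovery rates the mean slope difference was about 0 at every delay (−0.003 to 0.002).

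**The case against.** The strongest reply is that the plan's named primary analysis is the mixed model and not a test on the last ICU score. A reader might infer from step 3 that the planned analysis falls from 71% to 10% power. The documents do not support that. The drop belongs to a t-test suggested by the endpoint wording and the undated change in the sample-size text. A likelihood-based mixed model uses every daily score and can tolerate discharge that depends on recorded GCS, provided its mean and covariance are right. That proviso is the difficulty: only a patient-level random effect is named, and the ceiling at 15 is not addressed.

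A reader might also infer that the trial cannot say how much better consciousness was on a given day. That is too strong. In the step 3 setting, carrying the ICU-discharge score forward to day 7 gave 1.29 v 1.31 points and 69% v 71% power. A stated rule would largely suffice if patients leave ICU near-normal and none dies. The plan has no such rule, and neither condition is assured.

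Part of the slope distortion comes from fitting a straight line to a capped score, and not from where collection stops. This stands, and it is why the fix changes the model as well as the data collection.

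Speed of recovery is also covered by secondary end points and the planned Kaplan-Meier and Cox analyses, so an effect need not go unseen, though these are not primary. Inverse probability weighting is listed as a sensitivity analysis and might help, but its target is unstated. Finally, patients may enter for prolonged ventilation alone, so a baseline GCS near 8 need not hold.

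**Conclusion.** The point holds as a defect in how the primary outcome is defined and observed. The window ends at an event that recovery probably brings about, no common day is named, and the linear model supplies no contrast day. If the drug works, change to ICU discharge understates it (0.3 v 1.3 points in one illustrative setting, 0.24 to 0.46 v about 0.95 in another). The mixed-model slope reflects discharge timing, the random-effects form and the ceiling as well as the drug, although power need not fall.

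A reader might infer that the design favours levothyroxine. It does not: with equal recovery and the same discharge practice in both arms there was no directional bias. That is not a guarantee of the nominal false-positive rate. In the second setting the random-intercept model rejected a true null in 26% to 36% of trials cut at discharge, but also in 23% to 28% with full follow-up. That excess is therefore mainly a matter of omitting random slopes and is separate from this point.

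The mechanism rests on the inferred link between recovery and discharge. Every size rests on assumed baselines, recovery rates, discharge rules and no deaths, none of which the documents give. The change is one the sponsor should make.

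**What to change.** 1. Define the primary endpoint as the between-arm GCS difference at one fixed day after allocation, chosen by the sponsor, and report ventilation/SBT status at the same day.
2. Estimate it as the arm contrast at that day from the mixed model with day as a category, replacing the linear arm-by-time slope.
3. Obtain GCS and ventilation/SBT status at that day for every randomised patient, including those already on the ward. Where no ward score exists, use the last ICU or hospital-discharge score under a written rule, with a sensitivity analysis for patients who leave impaired.
4. State how deaths before that day are handled.
5. Keep improvement up to ICU discharge as a descriptive result.

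The cost is protocol and SAP wording plus a few bedside scores, possibly made by a different clinician from the one scoring in ICU. The sample size needs no change: 25 per arm stands for a GCS change of 0.80 SD at a common day. If follow-up has already ended, as the past tense in the sample-size text may suggest, ward GCS should be retrieved where recorded and the limitation reported.

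### The second free T3 sample and the echocardiogram have no fixed or ordered study days, so the planned free T3 mediation of EF can be biased in either direction

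*Combined protocol and SAP*

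**What the plan says.** Thyroid profile appears twice in section 3 (METHODOLOGY), in the ICU text under Anesthetic management. The first is part of the metabolic work-up of delayed recovery, before patients are split into groups. The second is "Assessment of thyroid profile (free T3, free T4, TSH) before hospital discharge". No sample is set between these, and the second has no study day.

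Among the secondary end points is "Improvement of cardiac function by echocardiography", again with no day. Total hospital stay is also a secondary end point. By contrast, GCS and the breathing trial are assessed daily until ICU discharge.

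The Statistical Analysis section states: "The Sobel test quantified the proportion of EF preservation attributable to changes in free T3". It names no covariates for this analysis. Inverse probability weighting is listed only as a robustness check and is not tied to the mediation. No handling is given for patients without a second thyroid value.

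**The concern.** A mediation analysis needs the mediator measured before the outcome, at a time that the outcome does not determine. On this schedule the change in free T3 can only be the second value minus the work-up value. If the second sample is drawn close to discharge, it comes early in fast recoverers and late in slow ones. Time since surgery, any accumulated exposure, and recovery itself then all enter the mediator. A patient who dies in hospital may have no second value. Because the echocardiogram is undated, nothing makes free T3 precede EF.

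At stake is the mechanistic conclusion: a statement that some share of EF preservation is attributable to free T3, or that free T3 plays no part or an adverse one, when the data cannot tell these apart.

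**Working it through.** **The plan's own figure.** The Sample Size sections give "setting power at 80% and alpha error at 0.05", "using two-sized a z test" (read as two-sided) and "detecting an effect size of 0.80 in GCS change". Then n per arm = 2 × (1.960 + 0.842)² / 0.80² = 24.53, rounded up to 25. This reproduces the stated "sample size of 25 patients per group total 50 patients". The enrolled number is 35 per arm. Neither figure is in dispute; 35 per arm is used below.

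**Common set-up.** The documents give no stay distribution, free T3 response, EF effect or correlations, so every input below except 35 per arm is an assumption. Free T3 has no effect on EF in any scenario. Path a is treatment on free T3 change; path b is free T3 change on EF given treatment. Sobel z = ab / √(a²·SE(b)² + b²·SE(a)²), compared with 1.96, in line with "All tests were two-tailed".

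**1. Stay-driven sampling alone.** Post-dose stay is log-normal with median 10 days and log SD 0.6, and log stay has correlation r with EF change. In treated patients free T3 rises by (plateau rise) × (1 − 2^(−t/7)) at sampling day t, with noise SD 0.7 in both arms. The 7-day half-life, and dosing that lasts until the sample, are assumptions. For half-lives of 5, 7 and 9 days, the fraction of plateau reached is:

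| Day | 5 days | 7 days | 9 days |
|---|---|---|---|
| 5 | 50% | 39% | 32% |
| 10 | 75% | 63% | 54% |
| 30 | 98% | 95% | 90% |

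Day 30 is thus 2.0 to 2.8 times day 5. False rejection with a 7-day half-life:

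| Plateau rise | r = −0.3 | r = −0.5 | r = −0.7 |
|---|---|---|---|
| 1 unit | 3% to 6% across the three r values | | |
| 2 units | 10% | 16% | 29% |
| 3 units | 14% | 30% | 53% |

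Nearly all these rejections are of negative sign. Longer stay gives a larger free T3 rise and goes with poorer EF, so b < 0 while a > 0. At r = −0.5, positive rejections were at most 0.5% of trials. With one fixed sampling day, rejection is at most about 5%. Rejection is higher if free T3 also drifts upward with time in both arms.

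**2. Shared recovery factor.** A recovery factor loads λ on both free T3 change and EF (each with within-arm variance 1). Treatment shifts free T3 by 1 SD and EF directly by 0.5 SD. Then b = λ², the false indirect effect is 1 × λ², and the apparent proportion mediated is λ²/0.5. For λ = 0.3, 0.5 and 0.7 this is 18%, 50% and 98%. The simulated proportions were 18%, 50% and 97%, with rejection in 7.0%, 43.6% and 96.1% of trials. These rejections are almost all positive.

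**3. Reversed order.** EF is read first and influences later free T3 with coefficient γ (other free T3 noise SD 0.8, same treatment effects). Then a = 1 + 0.5γ and b = γ/(γ² + 0.64). For γ = 0.3, ab = 1.15 × 0.3/0.73 = 0.47, against a total effect of 0.5. In simulation the proportion mediated was 93% and rejection 82%. For γ = 0.5 these were 139% and 99.6%. All rejections are positive.

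**4. What a fixed day does not cure.** With a shared factor of loading 0.6 and a fixed sampling day, unadjusted false rejection is still about 76%. Adjusting for a severity measure correlated 0.5, 0.8 or 0.95 with recovery lowers it to 60%, 21% and 5%. Under the assumed stay distribution, Φ((ln 5 − ln 10)/0.6) = Φ(−1.155) = 12% of patients would leave before a day-5 sample, and with r negative these are mainly the fast recoverers.

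**The case against.** The strongest reply is that the text says less than it may seem to say. A sample before discharge has a latest time, not a set time, so one taken soon after the first dose would comply. The documents give no treatment duration, so dosing up to discharge is an inference, and the half-life comes from outside them. The simulated percentages depend heavily on the assumed free T3 rise; with a small rise there is no material inflation. The mediation is neither the primary analysis nor a listed end point. The Statistical Analysis section is in the past tense and reports enrolment, so moving the samples may no longer be possible.

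All of this stands, and it limits the point to timing left open and to a conditional size. It does not remove the point: a sample that may fall on any day up to discharge is still not protected from following recovery, and nothing orders it before the echocardiogram.

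A reader might infer that discharge-timed sampling would manufacture a favourable free T3 pathway. The calculations do not support that: timing alone gives mainly negative-sign results, and a false favourable result needs a shared recovery factor or reversed order. A reader might also infer that the trial has no baseline thyroid value. It has one, from the work-up before allocation.

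**Conclusion.** The point holds in this form: the day of the only post-allocation free T3 sample and the day of the EF echocardiogram are both open, so the sample can track recovery and EF can precede the mediator. The planned claim of a share attributable to free T3 is not supported by this schedule.

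The bias may run either way. Its size cannot be fixed from the documents: stay-driven timing alone spans about 5% to more than 50% false rejection, depending on the assumed free T3 rise and EF–stay correlation. The shared-factor and reversed-order figures are equally conditional. It would go too far to say that the mediator is measured after its outcome; the documents allow this but do not show it. The primary GCS model and the sample size are untouched.

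**What to change.** **If sampling can still be changed**
- Take the existing second thyroid sample at one fixed day after the first dose, in every patient still in hospital. Define free T3 change as that value minus the pre-allocation value.
- Take the EF echocardiogram at a fixed later day.
- Adjust both mediation models for baseline free T3, baseline EF where available, and severity. A fixed day without this adjustment leaves the confounding in scenario 2 in place.
- Report the mediation as exploratory, without an attribution claim.

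**If sampling is complete**
- Report the actual sampling and echocardiogram days by arm.
- Adjust for sampling day, and exclude from the mediation any patient whose EF precedes the free T3 sample. In the stay-driven model, adjusting for log stay brought false rejection to about 5% or less. Both steps condition on events after allocation, which is a further reason to label the result exploratory.

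**Cost.** The number of tests is unchanged; the first route needs protocol wording and scheduling. Patients who die or are discharged before the fixed day have no mediator value (about 12% discharged before day 5 under the assumed stay distribution), and these should be counted and reported. The discharge thyroid value is lost unless an extra tube is drawn; if kept, it should be descriptive only.

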Official Title: Role of Levothyroxine Supplementation in Delayed Recovery Following Cardiac Surgery

NCT Number: NCT06660823

Document Date: November 1, 2024

Protocol Of A Paper For Partial Fulfilment Of Research In Anesthesia, ICU and pain management

The title: Role of Levothyroxine supplementation in delayed recovery following cardiac surgery.

NAME OF RESEARCHER: [name]

Academic Position: lecturer of Anaesthesia, Intensive Care and Pain management

Department: Faculty of Medicine-Ain Shams University

NAME OF RESEARCHER: [name]

Academic Position: Lecturer of Anaesthesia, Intensive Care and Pain management

Department: Faculty of Medicine-Ain Shams University

**Faculty of Medicine
Ain Shams University
2024**

1. INTRODUCTION/ REVIEW (Maximum 1000 words) *“References are needed”*

Research indicates that hypothyroidism decreases heart contractility, reduces stroke volume and rate, affects the vascular endothelium, and increases the risk of atherosclerosis, systemic vascular resistance, hypertension [1], atherogenic lipid profile, and coagulation abnormality [2].

Hypothyroidism was reported to be strongly related to cardiovascular disease, respiratory complications, neurological complications, and a significant difference in ventilator weaning time [3].

Severe thyroid dysfunction is related to muscle relaxation and lead to respiratory muscle depression and disturbed conscious level.[3]

Surgical stress of cardiac surgery might be followed by a prolonged recovery process and cardiac dysfunction [3].

The exact physiology of thyroid disease and the relationship with post cardiac surgery remain unclear. Thus far, large-scale clinical statistical analysis evidence on the complication rate and long-term mortality is lacking. Current important prognostic assessment tools such as EuroSCORE II [4], and Society of Thoracic Surgeons (STS) score [5] do not include thyroid function assessment, even though it has a significant impact on the metabolic, cardiovascular, and circulation system.

2. AIM/ OBJECTIVES (Maximum 300 words)

The primary aim of this study is to investigate the effect of supplementation of oral levothyroxine in delayed recovery patients post cardiac surgery.

3. METHODOLOGY:

Patients and Methods/ Subjects and Methods/ Material and Methods (Maximum 1000 words) "References may be needed"

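### The primary endpoint and its GCS model give no weight to death in the ICU, so an arm with more deaths can still win on the primary

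*Combined protocol and SAP*

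**What the plan says.** Under Endpoints of the study, the primary endpoint is "Improvement of Glasgow coma scale and spontaneous breathing trial before ICU discharge". The schedule, in the Methodology section, is "Daily assessment of conscious level according to Glasgow Coma Scale (GCS) and spontaneous breathing trial by ICU consultant till ICU discharge". It sets no fixed assessment day and does not mention death.

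Under Statistical Analysis, the only primary analysis is: "Linear mixed-effects regression modeled GCS trajectories over time, with group, time, and their interaction as fixed effects and patient as a random effect". Four other statements might be expected to deal with deaths:

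- The analysis set: "Analyses adhered to the intention-to-treat principle".
- The sensitivity analysis: "Inverse probability weighting assessed robustness", without saying what is weighted.
- The time-to-event line, which plans Kaplan-Meier and Cox analyses but names no event.
- The sample-size text: "To ensure adequate power for secondary endpoints and allow for dropouts, we enrolled 35 patients per group", which gives no dropout rate and does not mention deaths.

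The secondary endpoints are ventilation time, ICU stay, hospital stay, inotropic support and echocardiographic function. Mortality is not among them. The Introduction mentions it only as background ("evidence on the complication rate and long-term mortality is lacking").

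**The concern.** Patients are randomised because they are still ventilated or not fully conscious 48 hours after on-pump surgery, and emergency cases are eligible. Some deaths in the ICU are foreseeable.

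A likelihood mixed model uses the GCS values that exist and treats the rest as ignorable missing data. After a death it behaves as though the patient had gone on recovering unobserved. If patient is a single random effect (a random intercept, the plainest reading of the plan), the implied course follows the arm's common slope. Only if a random slope is added is it pulled towards the patient's own slope.

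Either way, the worst failure to recover does not count as a failure. If the slowest recoverers die, their records are also shorter and pull less on the arm's slope. A significant group-by-time term could then be reported as better recovery in an arm where more patients died. Nothing else in the plan obliges the authors to show those deaths alongside it.

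**Working it through.** **1. The plan's own figure.** For effect size 0.80, two-sided alpha 0.05 and 80% power, n per arm = 2 × (1.960 + 0.842)² / 0.80² = 15.70 / 0.64 = 24.5, so 25. The stated figure reproduces with the z formula; the exact t-test gives 26. With 35 per arm the z power is 91.7%. None of this involves deaths.

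**2. Does any statement score a death?**

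- Intention-to-treat keeps the patient in the analysis set but supplies no value after death.
- Weighting is unspecified. Even if it were weighting for death, it would let survivors stand in for the dead rather than count the death.
- The Cox line names no event.
- The dropout remark concerns sample size only.

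The gap is therefore in the plan itself.

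**3. Size, by simulation.** From the documents: 35 per arm, daily GCS, group, time and their interaction, two-sided 0.05, Mann-Whitney test. Assumed: GCS followed to day 10, baseline 7 (SD 2), slope 0.4 (SD 0.4) points per day, scores rounded and held within 3 to 15, deaths on days 2 to 8 among the poorest trajectories. Deaths of 30% v 15% mean 0.30 × 35 = 10.5 against 0.15 × 35 = 5.25 expected per arm. There were 500 trials per case.

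| Case | Analysis | Deaths 15% v 15% | Deaths 30% active v 15% control |
|---|---|---|---|
| GCS benefit 0.25/day | Mixed model, random slope: favours active | 43% | 40% |
| GCS benefit 0.25/day | Day-10 rank test, death worst: favours active | about 37% | 10% |
| No GCS effect | Mixed model, random intercept: active better / worse | 22% / 23% | 44% / 8% |

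- *Row 1.* The change is −3 points. Its Monte Carlo standard error is √(0.43×0.57/500 + 0.40×0.60/500) = 3.1 points, so doubling active-arm deaths makes no detectable difference. A 1,000-trial run gave 39% and 43%. The level near 40% is not the trial's power: in the 1,000-trial run the variances were held at their generating values, which is conservative. Estimating them raises both entries together.
- *Row 2.* The change is −27 points, with standard error √(0.37×0.63/500 + 0.10×0.90/500) = 2.5 points.
- *Row 3.* The 22% and 23% are already inflated, because the simulated slopes vary and a random intercept ignores that. The effect of deaths is the asymmetry, 44% against 8%.

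**4. Different assumptions.** A second set used baseline 8 (SD 2), slope 0.5 (SD 0.3), residual SD 1, deaths on days 2 to 6, and records ending at discharge.

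- No GCS effect, slowest recoverers die, 30% v 10%, random intercept: active better in 50% and worse in 4%, against 17% and 18% with no deaths.
- The same at 20% v 10%: 31% and 13%.
- The same at 30% v 10% with a random slope: 9% and 1%.
- GCS benefit 0.2/day, deaths 30% v 10% unrelated to GCS: active wins in 62% (random slope) to 81% (random intercept). The death-worst rank test favours active in 1–3% and goes against it in about 9%.

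**The case against.** The strongest reply is that the mixed model answers a legitimate question about consciousness while alive, and that the rank test answers a different one combining survival with consciousness. On this view, much of the gap between 40% and 10% is a difference of estimand under an assumed imbalance that the documents give no reason to expect. That is fair. It is why the numbers are illustrative and why the rank test is proposed beside the model and not in its place. It does not remove the gap, because the plan neither states the while-alive meaning nor commits to showing deaths by arm.

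Four stronger readings are tempting, and the documents do not support them.

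- *A patient who dies has no score.* GCS is recorded daily, so every value up to death enters the model. What is lost is the death.
- *Death leaves the arm's GCS mean unchanged.* Low values before death stay in and pull the arm's fitted level down. With a random slope the bias in the estimate is also small: with no GCS effect and deaths 30% v 15%, it was +0.10 to +0.15 points at day 10 in favour of active. If deaths are unrelated to GCS, the slope is not biased at all; the excess deaths are simply invisible.
- *The step from 25 to 35 allows for 10/35 = 29% deaths.* The plan attributes it to power for secondary endpoints as well as to dropouts, and gives no rate for either.
- *A death-ranked test costs no power.* That held only when every survivor was scored at day 10. Once discharge ended the record, at equal 15% deaths, ranking the last ICU GCS favoured active in 32% of trials against 62% for the mixed model, because discharge scores cluster near the top.

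**Conclusion.** The concern holds in this form: as written, the primary endpoint and its model give no weight to death in the ICU, mortality is not an endpoint, and an arm with more deaths can still win on the primary. That follows from the text and needs no assumed figure.

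The size does rest on assumptions: the death rates, the link between death and slow recovery, and the form of the random effect. With a random slope, the main harm is that excess deaths leave the chance of a win essentially unchanged. With a random intercept there is also a real tilt towards the arm with more deaths, provided the slowest recoverers are the ones who die. If deaths turn out few and balanced, the primary result is little affected. The plan should not depend on that.

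**What to change.** Keep the mixed model and add text along these lines under Statistical Analysis:

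1. The mixed-model result describes GCS while the patient is alive in the ICU. ICU deaths are reported by arm next to it.
2. As one supportive analysis, all randomised patients are compared on a single fixed, prespecified day by the Mann-Whitney test. Death by that day ranks below GCS 3. A patient discharged alive takes the discharge GCS (or is ranked at the top; state which). A patient still in the ICU takes that day's GCS.
3. Improved recovery is not concluded if this comparison points the other way.

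The random-effect structure should be stated at the same time, since the size of the problem depends on it. The breathing-trial half of the endpoint also lacks a rule for death, and the stated primary model does not analyse it. The analysis text is in the past tense; if unblinded results have already been seen, label the added comparison as such.

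The cost is a few sentences and one test on data already collected. The downside to state openly is that the supportive test mixes survival with consciousness and can have less power than the mixed model when discharge scores cluster near the top.
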